1 PROTOCOL SUMMARY

1.1 Protocol Synopsis

Objectives and Endpoints

Primary Objectives	Primary Endpoints	
To assess the safety and tolerability of RP-1664 in participants with eligible, advanced solid tumors	Incidence and severity of treatment-emergent adverse events (TEAEs)	
To define a dose and schedule of RP-1664 that is tolerated and has clinical activity	Dose and schedule based on safety, pharmacokinetic (PK), pharmacodynamic, and available efficacy data	

Overall Design

Several key aspects of the trial design are summarized below.

Intervention Model:	N/A	Population Type:	Adolescent (United States [US] only) and adult participants
Control:	None	Population Diagnosis or Condition:	Advanced solid tumors
Active Comparator:	N/A	Population Age:	Minimum: 12 years (US only; ≥ 40 kg if less than 18 years except participants with neuroblastoma must weigh ≥ 30 kg); 18 years—
			Maximum: N/A
Trial Intervention Assignment Method:	N/A	Site Distribution:	Multi-site and multi-regional

Number of Arms: 1

[figure not shown]
Blinding: Not applicable (no blinding).

[figure not shown]
Number of Participants: Approximately 80 evaluable participants (planned)

Trial Duration: Approximately 36 months

This is a multicenter, open-label Phase 1 trial to investigate the safety, PK, pharmacodynamic, and preliminary efficacy of the Polo-Like Kinase 4 (PLK4) inhibitor RP-1664 in participants with molecularly selected advanced solid tumors. The trial is estimated to enroll approximately

80 evaluable participants (definition of evaluable participants provided in Section 9.1) with solid tumors harboring any one of the following:

BID = twice daily; MTD = maximum tolerated dose; PD = pharmacodynamic; PK = pharmacokinetic; QD = once daily; SRC = Safety Review Committee

The trial will follow a Bayesian Optimal Interval (BOIN) design to guide escalation and deescalation decisions, establish a maximum tolerated dose (MTD), and to identify a dose and schedule of RP-1664 that is tolerable and has clinical activity. All participants will undergo a dedicated PK evaluation period starting at Cycle 0 Day 1 and will be assigned to receive either:

- A single dose of RP-1664 given as an adolescent/adult whole capsule at the highest Safety Review Committee (SRC) approved dose level with PK collection over the subsequent 48 hours to characterize the t_{1/2} of RP-1664 in the fasted state, or

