- 2) Two doses of RP-1664 as pediatric sprinkle capsules, one in the fed-state (with a high-fat meal) and one in the fasted-state (RP-1664 sprinkled over soft food), to examine the effect of food on RP-1664 PK, or
- 3) Two doses of RP-1664, one as the adolescent/adult whole capsule and the other as a pediatric sprinkle capsule, to compare the PK of the two formulations.

After completion of Cycle 0, participants will begin C1D1 at the assigned, SRC-approved dose and schedule being tested.

The starting dose (Dose Level 1) is anticipated to be 10 mg once daily (QD), when calculated based on the principles outlined in the International Conference on Harmonization (ICH) S9 Nonclinical Evaluation of Anti-cancer Pharmaceuticals (Section 2.2.6). Since neutropenia has been observed in preclinical safety studies and is an anticipated toxicity in humans, RP-1664 will initially be given QD on a 2 weeks on/1 week off schedule to allow 1 week for bone marrow recovery. Since the projected efficacious dose of RP-1664 in humans is approximately 300 mg QD (based on preclinical models), the first escalation (Dose Level 2) will be up to 30 mg to limit the number of participants receiving a potentially sub-therapeutic dose. After Dose Level 2, escalation will proceed with up to 100% increases in RP-1664 after evaluation of tolerability by

the SRC until Dose Level S. Dose Level S is defined as the dose level at which any of the following safety signals occur during Cycle 0 or Cycle 1:

- Any ≥Grade 3 hematological toxicity, or
- >50% decrease in platelets or neutrophils from Cycle 0 Day 1, or
- >2 g/dL decrease in hemoglobin from Cycle 0 Day 1, or
- Any ≥ Grade 2 drug-related non-hematological toxicity lasting >5 days or requiring clinical intervention, except Grade 2 fatigue, nausea, vomiting, diarrhea, or constipation, or
- Any adverse event (AE) of any grade limiting tolerability as assessed by the SRC

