At Dose Level S, the cohorts will be expanded to a minimum of 3 participants to further evaluate safety, PK, and pharmacological activity. Evidence of pharmacologic activity can include Grade ≥ 2 drug-related toxicity at any cycle, PK data demonstrating exposure levels predicted to be efficacious based on nonclinical studies, or other evidence of treatment-related activity as agreed on by the SRC. Dose decisions will be based on assessments in 2 or more dose-limiting toxicity (DLT) evaluable participants completing the DLT evaluation period. Any escalation of RP-1664 after Dose Level S will be in increments up to 75% as agreed upon by the SRC and will enroll cohort sizes of N \geq 3.

RP-1664 Escalation

	Escalation Plan	
Dose Level	Daily (mg) or % of previous dose increment	
1	10 mg	
2	Up to 30 mg	
3 to S	Up to 100% increases until Dose Level S	
S	Expand cohort at same dose	
S1 to MTD or tolerated and pharmacologically active dose	Up to 75% increases until MTD or tolerated and pharmacologically active dose	

Additional treatment schedules, including daily dosing, 3 days on/4 days off, 1 week on/1 week off, or 2 weeks on/2 weeks off may also be explored to mitigate AEs and/or improve efficacy. If an additional schedule is tested, the starting dose of RP-1664 may be as high as the highest total daily dose that cleared DLT evaluation. The decision to test one or more of these schedules and set the starting dose level will be agreed upon by the SRC, and will take into consideration all available safety, efficacy, pharmacodynamic, and PK data.

Dose modifications, including adjustments to treatment frequency (e.g., QD to BID or BID to QD dosing), schedule changes, or intra-participant dose escalations, will be allowed for participants to manage AEs and/or maximize RP-1664 exposure and clinical benefit. These changes in doses or schedules will be allowed only to previously SRC-approved levels or frequencies that have been cleared for DLT evaluation.

The food effect portion of the trial will be conducted at selected centers and may start at Dose Level 3 or once Dose Level S is reached. The fasting recommendation for RP-1664 in the general trial population may be revised to allow dosing with food after the PK profiles of 12 evaluable participants have been analyzed.

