- 15. Prior treatment with a PLK4 inhibitor.
- 16. Use of radiotherapy (except for palliative reasons) within 14 days prior to trial treatment initiation.
- 17. Current treatment with medications that are known to prolong the QT interval
- 18. Participants who are receiving strong P-glycoprotein (P-gp) inhibitors and/or breast cancer resistance protein (BCRP) inhibitors within 14 days prior to first dose of trial intervention

Note: RP-1664 is an in vitro inducer of CYP3A, CYP2B6, and CYP1A2. Investigators should consult with the Medical Monitor prior to enrollment of participants taking sensitive substrates of these enzymes, in particular CYP3A Participants must use additional methods of contraception if using estrogen/progestin-based agents.

Note: RP-1664 is a substrate of CYP1A1. Literature examples of CYP1A1 inhibitors are limited and the existence of clinically relevant CYP1A1 inhibitors are also limited. If investigators have questions with regards to particular concomitant medications, they should contact the Sponsor

- 19. Major surgical procedures ≤ 28 days prior to trial treatment initiation, Participants must have recovered from any of the effects of any major surgery. No waiting period is required following central venous access placement, biopsy collection or minor surgeries as long as Investigator assesses the impact on trial participation.
- 20. Gastrointestinal abnormalities, including inability to take whole, intact oral medication, requirement for intravenous alimentation, prior surgical procedures affecting absorption including total gastric resection or lap band, active inflammatory gastrointestinal disease, chronic diarrhea, symptomatic diverticular disease, treatment for active peptic ulcer disease in the past 6 months, and malabsorption syndromes.
- 21. Participants who are breastfeeding at screening or planning to become pregnant (self or partner) at any time during trial participation.
- 22. Psychological, familial, sociological, or geographical conditions that do not permit compliance with the protocol and/or follow-up procedures outlined in the protocol.

Trial Interventions

RP-1664 adolescent/adult whole capsules will be supplied as immediate-release solid dosage form for oral self-administration. The pediatric drug product for the Food Effect and PK Bridging portion of the trial will be supplied as sprinkle capsules.

Committees

Independent Committees: SRC.

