14.1.1 Schedule of Activities

Table 1 Schedule of Activities for Participants Enrolled on 2 Weeks On/1 Week Off Dosing (21-Day Cycles)

						Cyc	e 0														
	Pre- screening						Food Effect or ing Cohorts							Cycle 2			Additional Cycles		EOT/ ET°	Safety	Survival Follow- up ^e
		Screening ^a	Ef For	d (Fo fect) mula l (Pl ridgi	or ation K	Ef Forn	Fasted (Food Effect) or Formulation 2 (PK Bridging)					Cycle	1							Follow -up Visit ^d	
Trial Days	-180 to -1	-28 to -1	1ª	2	3 4	5 (+5)	6	7	8	1ª	1	8 (+2)	15 (+2)	1 (+3)	8 (+2)	15 (+2)	1 (+3) ^g	8 (+2) ^h	Within +7 days of Disc of	30 days after last	Every 90 days (±14 days)
Procedures/ Assessments ^f																			Trt date	dose (+14 days)	
Pre-screen informed consent	X																				
Screening/mai n informed consent		X																			
Inclusion/ exclusion criteria		X	X							X											

	Pre- screening	Screeninga				Cycl	e 0														
			PK	PK Cycle For Food Effe PK Bridging Cohor						PK Cycle ^b									EOT/	Safety Follow	Survival
			Ef For	d (Fo fect) mula 1 (PK ridgin	or tion	Fasted (Food Effect) or Formulation 2 (PK Bridging)				Fasted		Cycle	e 1	Cycle 2				tional cles	EO17	-up Visit ^d	Follow- up ^e
Trial Days	-180 to -1	-28 to -1	1ª	2	3 4	5 (+5)	6	7	8	1ª	1	8 (+2)	15 (+2)	1 (+3)	8 (+2)	15 (+2)	1 (+3) ^g	8 (+2) ^h	Within +7 days of Disc of Trt	30 days after last	Every 90 days (±14 days)
Procedures/ Assessments ^f																			date	dose (+14 days)	
Molecular eligibility ⁱ	X																				
Demographics	X																				
Medical/cance r history		X																			
Physical examination		X	X							X									X		
Abbreviated PE ^j														\mathbf{X}^{j}			\mathbf{X}^{j}			X	
Height ^k		X															X^k				
Weight		X	X							X				X			X		X	X	
Vital sign measurements ¹		X	X							X	X	X	X	X	X	X	X	X ^h	X	X	

							Cycle	e 0														
	-		PK	Cy PK	/cle K Br	For idgi	· Food I ing Coh	Effe	ct o	r	PK Cycle ^b							Additional		EOT/	Safety	Survival
	Pre- screening	Screening ^a	E1 For B1	1 (P ridg	t) or latio 'K jing)	Fasted (Food Effect) or Formulation 2 (PK Bridging)				Fasted		Cycle	:1	Cycle 2				tional cles	ET°	Follow -up Visit ^d	Follow- up ^e	
Trial Days	-180 to -1	-28 to -1	1ª	2	3	4	5 (+5)	6	7	8	1 ^a	1	8 (+2)	15 (+2)	1 (+3)	8 (+2)	15 (+2)	1 (+3) ^g	8 (+2) ^h	Within +7	30 days	Every 90 days
Procedures/ Assessments ^f																				days of Disc of Trt date	after last dose (+14 days)	(±14 days)
ECOG or Lansky performance status		X	X								X				X			X		X	X	

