- o. Clinical Safety Laboratory Tests: Clinical laboratory tests (including serum or plasma chemistry, hematology [including reticulocyte count], and urinalysis) will be performed at local laboratories according to the laboratory's normal procedures. See Section Error! Reference source not found. for a complete listing of laboratory tests to be performed.

- q. **Baseline Tumor Biopsy:** If archival tissue does not meet trial requirements, a pre-treatment biopsy during Screening is mandatory. If a biopsy cannot be safely performed, the participant may still be eligible with prior Sponsor approval. If the participant is providing paired biopsies, a pre-treatment and an on-treatment biopsy are mandatory. Biopsy tissue must be shipped to the Sponsor-designated lab during Screening or by Cycle 1 Day 1 (+7 days). Bone tissue is not acceptable for tumor tissue submission because bone biopsies require a decalcification step that will interfere with downstream processing of the sample. *US only:* Participants 12 to 17 years of age are not required to provide a biopsy.
- r. **On-treatment Tumor Biopsy**: This assessment applies only to participants providing a paired tumor biopsy. Biopsy should be collected on Cycle 2 Day 8 (+2), 2 to 6 hours after dosing of RP-1664. Participants must have taken a minimum of 7 consecutive days of RP-1664 prior to on-treatment biopsy collection. If biopsy collection at this timepoint is not possible, please contact the Sponsor to schedule an appropriate time for on-treatment biopsy.
- s. **Post-Progression Tumor Biopsy:** An optional tumor biopsy will be requested post-progression for participants with prior confirmed responses or stable disease ≥ 16 weeks.
- t.
- Mandatory Archival Tumor Tissue: Archival tissue is to be submitted to the Sponsor-designated lab during Screening. Refer to Laboratory Manual for further details. If adequate archived tumor tissue is not available and/or a fresh biopsy cannot be safely performed, the participant may still be eligible with prior Sponsor approval. The Sponsor prefers archival material from the primary tumor if available.
- v. **RP-1664 Administration:** Cycle 0 dosing should start Monday to Wednesday, if unable to accommodate weekend visits. A +5-day window is allowed prior to initiating the Cycle 0 Day 5 Fasted PK or PK bridging blood collection.

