- w. Review of Dosing Diary: Dosing diary will be reviewed at each participant visit and collected at each CXD1 visit and at EOT. Additional details are in the Pharmacy Manual

- bb. Urine Collection: Urine collection is only required for participants in the food effect portion of the trial. Urine samples will be collected (0 to 3, 3 to 6, and 6 to 12 hours) while participants are in the clinic on Cycle 0 Day 5.
- cc. **Tumor Assessment:** Tumor assessments by disease-appropriate standard criteria (e.g., RECIST v1.1 or INRC) using CT/MRI of known sites of disease as clinically indicated. Tumor assessments must be performed at Screening and every 6 weeks (±7 days) from C1D1 for the first 3 assessments, or sooner if clinically indicated). Thereafter, assessments must be performed every 9 weeks (±7 days). Per RECIST v1.1, complete response or partial response should be confirmed; tumor imaging for confirmation of response must be performed at least 4 weeks after the first indication of response. The subsequent tumor imaging after the confirmation of response should be obtained per the original scheduled interval from the confirmatory scan (6 weeks ± 7 days during the first ~5 months of trial treatment or every 9 weeks thereafter). If a participant discontinues treatment for a reason other than radiographic disease progression, withdrawal of consent to trial, lost to follow-up, or death, scans should continue at the specified intervals until progression is confirmed or until start of subsequent anticancer treatment. All radiographic images/scans at the timepoints specified as well as any unscheduled images/scans should be archived by the trial sites for potential future evaluation.
- dd. **Tumor Assessment at Screening:** Scans performed prior to signing of the ICF as part of routine clinical management are acceptable for use as baseline tumor imaging if they are of diagnostic quality and performed within 28 days prior to the first dose on Cycle 0 Day 1.
- ee. **Serum Tumor Markers:** This assessment applies only to participants with cancers being monitored by circulating tumor markers (e.g., CA-125 or PSA). The baseline assessment should be performed within 96 hours of the first dose on Cycle 0 Day 1. If the assessment is done during Screening prior to this time, it should be repeated within the allotted time frame. It should then be collected on Day 1 of each subsequent cycle starting at Cycle 2, or per standard of care, through end of treatment.

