- cc. **Tumor Assessment:** Tumor assessments by disease-appropriate standard criteria (e.g., RECIST v1.1 or INRC) using CT/MRI of known sites of disease as clinically indicated. Tumor assessments must be performed at Screening and every 6 weeks (±7 days) from C1D1 for the first 3 assessments, or sooner if clinically indicated). Thereafter, assessments must be performed every 9 weeks (±7 days). Per RECIST v1.1, complete response or partial response should be confirmed; tumor imaging for confirmation of response must be performed at least 4 weeks after the first indication of response. The subsequent tumor imaging after the confirmation of response should be obtained per the original scheduled interval from the confirmatory scan (6 weeks ± 7 days during the first ~5 months of trial treatment or every 9 weeks thereafter). If a participant discontinues treatment for a reason other than radiographic disease progression, withdrawal of consent to trial, lost to follow-up, or death, scans should continue at the specified intervals until progression is confirmed or until start of subsequent anticancer treatment. All radiographic images/scans at the timepoints specified as well as any unscheduled images/scans should be archived by the trial sites for potential future evaluation.
- dd. **Tumor Assessment at Screening:** Scans performed prior to signing of the ICF as part of routine clinical management are acceptable for use as baseline tumor imaging if they are of diagnostic quality and performed within 28 days prior to the first dose on Cycle 0 Day 1.
- ee. **Serum Tumor Markers:** This assessment applies only to participants with cancers being monitored by circulating tumor markers (e.g., CA-125 or PSA). The baseline assessment should be performed within 96 hours of the first dose on Cycle 0 Day 1. If the assessment is done during Screening prior to this time, it should be repeated within the allotted time frame. It should then be collected on Day 1 of each subsequent cycle starting at Cycle 2, or per standard of care, through EOT.
- ff. Post-trial Therapy Data Collection: All anticancer therapies with start and stop dates should be recorded for 6 months after treatment discontinuation.

[figure not shown]

Table 7: Schedule of Activities for Participants Enrolled on 1 Week On/1 Week Off Dosing (28-Day Cycles, if Needed)

				K Cycle For Foo Bridging (Fed (Food Effect) or			cle 0																

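### The food-effect cohort is dosed in one order only (fed on Day 1, fasted from Day 5), so the effect of food cannot be separated from a period effect

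*SAP*

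**What the plan says.** Protocol 1.1 gives food-effect participants, in Cycle 0, "Two doses of RP-1664 as pediatric sprinkle capsules, one in the fed-state (with a high-fat meal) and one in the fasted-state". It does not state which dose comes first. The synopsis also lists "Number of Arms: 1" and gives the assignment method as not applicable.

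The order appears in SAP 14.1.1, the same way in Tables 1, 3, 5, 7 and 9:

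- Cycle 0 Days 1 to 4 are headed "Fed (Food Effect) or" first formulation. The head is broken in Table 1 but legible in Table 7.
- Days 5 to 8 are headed "Fasted (Food Effect) or Formulation 2 (PK Bridging").
- The administration footnote ties Day 5 to the fasted state: "A +5-day window is allowed prior to initiating the Cycle 0 Day 5 Fasted PK or PK bridging blood collection".
- Urine is taken in the food-effect portion on Day 5 only: "Urine samples will be collected (0 to 3, 3 to 6, and 6 to 12 hours) while participants are in the clinic on Cycle 0".

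On use of the result, Protocol 1.1 says that the fasting recommendation for the general trial population "may be revised to allow dosing with food after the PK profiles of 12 evaluable participants have been analyzed". SAP 4.1 allows the same revision once at least 4 participants have been evaluated. These two statements need to be reconciled.

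On analysis, SAP 3 leaves pharmacokinetics to a separate plan that may be written. SAP 4.3 gives no variance, power or margin for the food effect. It calls the sample size adequate for a preliminary assessment.

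**The concern.** Each participant acts as their own control, which is the right basis for a small food-effect study. But if everyone takes the fed dose first, anything that differs between the first and second dosing occasion shifts the fed/fasted ratio. A change in the patient's condition over the 4 to 9 days between doses would do so, as would a change in concomitant medication, a difference in sampling conduct, or drug left from the first dose. The data would show a ratio and a confidence interval, and nothing in them would reveal how much of the ratio is food.

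The ratio feeds a decision about how all later participants take the drug. An apparent absence of food effect could be a real effect offset by a period shift, and an apparent effect could be no more than a period shift.

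**Working it through.** The plan states no figure for the food effect, so there is none to reproduce. The check has four steps.

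**1. Can food and period be separated?** Model log exposure as participant effect + π (Period 2) + τ (fed) + error.

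- Fixed order: every fed-minus-fasted difference has expectation τ − π. Only that combination can be estimated. The design matrix has rank 13 of 14 columns at n = 12 and 5 of 6 at n = 4, and the period and food columns correlate at −1.
- Balanced order: the differences have expectation τ − π in one sequence and τ + π in the other, and their average is τ. The rank is full: 14 of 14 at n = 12 and 6 of 6 at n = 4.

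**2. Size of the bias (illustrative period ratios, not from the documents).** In the fixed order, observed ratio = true fed/fasted ratio ÷ (Period 2/Period 1 ratio). With no food effect:

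| Period 2/Period 1 | Observed fed/fasted |
|---|---|
| 0.90 | 1/0.90 = 1.11 |
| 0.80 | 1/0.80 = 1.25 |
| 1.10 | 1/1.10 = 0.91 |
| 1.25 | 1/1.25 = 0.80 |

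**3. Comparison with sampling error (assumed within-subject CV).** σ = √ln(1 + CV²). The 90% confidence factor at n = 12, paired with 11 df, is exp(1.796 × σ × √(2/12)).

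- CV 20%: σ = 0.1980, factor 1.16
- CV 30%: σ = 0.2936, factor 1.24
- CV 40%: σ = 0.3853, factor 1.33

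At CV 30%, the log half-width is 0.215. A period ratio of 0.80 shifts the log estimate by ln 1.25 = 0.223, about the whole half-width. A ratio of 0.90 shifts it by 0.105, about half.

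**4. Carry-over, kept apart from period.** The half-life is not given, so a range is assumed. Fraction of drug left = 0.5^(gap ÷ half-life). The gap is 4 days (Day 1 to Day 5) and up to 9 with the window. For AUC with a true ratio g = 1.5 and fraction f left at 4 days, the fixed order reads g/(1 + gf) without correction. A balanced order reads √{[g/(1 + gf)] × (g + f)}.

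| Half-life (assumed) | Left at 4 days | Left at 9 days | Fixed order reads | Balanced order reads |
|---|---|---|---|---|
| 12 h | 0.4% | 0.0% | 1.49 | 1.50 |
| 24 h | 6.25% | 0.2% | 1.37 | 1.46 |
| 48 h | 25% | 4.4% | 1.09 | 1.38 |

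Balancing reduces the carry-over bias in this example but does not remove it, because the fed dose leaves more drug behind than the fasted dose.

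**The case against.** Four points can be made for the plan.

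*The effect may be nil.* No document shows a period effect, and the 0.90 to 0.80 range and the 30% CV are assumptions. This stands as a limit on size. It does not restore the ability to tell food from period.

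*Carry-over is probably small.* Sampling over 48 hours to characterise the half-life, and a half-life under 12 hours as one trigger for twice-daily dosing, suggest that a short half-life is at least possible. At 12 hours, 0.4% is left after 4 days. This also stands. Drug carry-over matters from about 24 hours upward, and it then pulls a positive food effect toward 1.

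*The purpose is modest.* SAP 4.3 speaks of a preliminary assessment, and the recommendation only may be revised. But the same result can change dosing conditions for the general trial population, and the remedy needs no more participants.

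*Not everything is visible.* Only the protocol synopsis is at hand, and Tables 11 and 12 are not shown. A randomised order elsewhere cannot be excluded, though it would contradict all five schedule tables. A Day 5 pre-dose sample may already be planned. It would help with residual drug but not with a period effect.

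A reader might go further and infer that enzyme induction makes a period effect likely, since Protocol 1.1 states that "RP-1664 is an in vitro inducer of CYP3A, CYP2B6, and CYP1A2". The documents do not support that step. The adjoining note names CYP1A1 as the enzyme of which the drug is a substrate, and CYP1A1 is not on the induced list. Nothing says that one dose changes the drug's own clearance days later.

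**Conclusion.** The point holds for the food-effect cohort. The order is fixed in every schedule table, and the confounding with period is complete whether 12 or 4 participants are used. It is a matter of design, so a later pharmacokinetic analysis plan cannot repair it. The size and direction of any bias are unknown. The figures of 1.11 to 1.25, against a confidence factor of 1.24, show only that a moderate period shift could be as large as the sampling error. They rest on the assumed period ratios and CV.

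Two wider readings are not supported. First, the bridging cohort shares the column heads, but Formulation 1 and Formulation 2 are not tied to a named capsule there, so a fixed bridging order is not shown. Second, a balanced order does not cure everything: it cancels an additive period effect, while unequal carry-over remains if the half-life is long.

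**What to change.** 1. Allocate food-effect participants not yet dosed 1:1 to fed-fasted or fasted-fed, and relabel the Cycle 0 columns in Tables 1, 3, 5, 7 and 9 as Period 1 and Period 2.
2. In the pharmacokinetic analysis plan, analyse log AUC and log Cmax with sequence, period and treatment terms.
3. Tie urine collection to the fasted period rather than to Day 5. Otherwise a mixed order would mix fed and fasted urine.
4. Confirm that a pre-dose sample is taken in the second period, and use it to check for residual drug.
5. For the bridging cohort, confirm whether the formulation order is fixed, and balance it only if it is.

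**Cost.** No added participants. With 6 per sequence, the variance of the food contrast is (σ²/2)(1/6 + 1/6) = 0.167σ², the same as 2σ²/12 under the fixed order. One residual degree of freedom goes to period: the t multiplier rises from 1.796 to 1.812, and the factor at CV 30% from 1.240 to 1.243. The allocation list and the wording of five schedule tables must be changed, which probably means a protocol amendment. If some participants have already been dosed fed-first, the split may be uneven. With 9 and 3, for example, the variance is (σ²/2)(1/9 + 1/3) = 0.222σ², less precise but still able to separate food from period. If all have been dosed, the report should state that the ratio includes any period effect.
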